### **3.6 Methods for ensuring blinding**

Investigators and study subjects will be blinded in the study. Matching placebo will be used to ensure the blinding.

### **3.7 Methods for unblinding**

Individual treatment codes, indicating the treatment randomisation for each randomised subject, will be available to the Investigator(s) or pharmacists at the study site, and the personnel who are independent to the study evaluation at the Sponsor.

The treatment code should not be broken except in medical emergencies when the appropriate management of the subject requires knowledge of the treatment randomisation. The Investigator documents and reports the action to Company, without revealing the treatment given to subject to the Company staff.

The Company retains the right to break the code for SAEs that are unexpected and are suspected to be causally related to an investigational product and that potentially require expedited reporting to regulatory authorities. Treatment codes will not be broken for the planned analyses of data until all decisions on the evaluability of the data from each individual subject have been made and documented.

### **3.8 Restrictions**

None.

### **3.9 Discontinuation of investigational product**

Subjects may be discontinued from the study medication due to adverse events.

#### **3.9.1 Procedures for discontinuation of a subject from investigational product**

A subject that discontinues will always be asked about the reason(s) for discontinuation and the presence of any adverse events. The Principal Investigator/Investigator will perform the best possible observation(s), test(s) and evaluation(s) as well as give appropriate medication and all possible measures for the safety of the subject. They will also immediately inform Sponsor of the withdrawal. Adverse events will be followed up (See Section 6); events will be recorded using CRFs and all unused study drug should be returned by the subject.

If an adverse event possibly related to the study drug is resolved, subjects will be allowed to re-start the study medication.

If a subject is withdrawn from study, see Section 3.10.

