#### **3.2 Exclusion criteria**

Subjects should not enter the study if any of the following exclusion criteria are fulfilled:

- (1) Contraindication to MRI
- (2) Currently or within last three months treatment with a SGLT2 inhibitor
- (3) eGFR  $<45$  mL/min/1.73 m^2
- (4) Unstable or rapidly progressive renal disease
- (5) Hypotension with SBP  $<100$  mmHg
- (6) Hypersensitivity to dapagliflozin or any excipients
- (7) Patients with severe hepatic impairment (Child-Pugh class C)
- (8) Patients with active hepatitis B or C infection
- (9) Any of the following CV/Vascular Diseases within 3 months prior to signing the consent at enrolment, as assessed by the investigator:
- (10) Myocardial infarction
- (11) Cardiac surgery or revascularization (CABG/PTCA)
- (12) Unstable angina
- (13) HF New York Heart Association (NYHA) Class IV
- (14) Transient ischemic attack (TIA) or significant cerebrovascular disease
- (15) Unstable or previously undiagnosed arrhythmia
- (16) Established PAD
- (17) Active bladder cancer
- (18) Recent episode of DKA, frequent episodes of DKA
- (19) High risk of fractures, amputations and fibrosis
- (20) Women of child-bearing potential (ie, those who are not chemically or surgically sterilized or who are not post-menopausal) who have a positive pregnancy test at enrolment or randomization, OR women who are not willing to use a medically accepted method of contraception that is considered reliable in the judgment of the investigator,

from the time of signing the informed consent until two weeks after the last dose of IP, OR women who are breast-feeding.

(21) Individuals with a high risk of fractures, known diagnosis of osteoporosis or osteopenia, and/or history of fracture due to degenerative bone disease.

Procedures for withdrawal of incorrectly enrolled subjects see Section 3.4.

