## **3.11 Discontinuation of the study**

The study may be stopped if, in the judgment of the Sponsor, trial subjects are placed at undue risk because of clinically significant findings that:

- meet individual stopping criteria or are otherwise considered significant
- are assessed as causally related to study drug
- are not considered to be consistent with continuation of the study

Regardless of the reason for termination, all data available for the subject at the time of discontinuation of follow-up must be recorded in the CRF. All reasons for discontinuation of treatment must be documented.

In terminating the study, the Sponsor will ensure that adequate consideration is given to the protection of the subjects' interests.

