### **6.7.1. Maternal exposure**

Women of childbearing potential are not allowed to be included in this study. Should a pregnancy still occur, the investigational product should be discontinued immediately and the pregnancy reported to the UW HSD and the funding agent, AstraZeneca,.

Pregnancy itself is not regarded as an adverse event unless there is a suspicion that the investigational product under study may have interfered with the effectiveness of a contraceptive medication. Congenital abnormalities/birth defects and spontaneous miscarriages should be reported and handled as SAEs. Elective abortions without

complications should not be handled as AEs. The outcome of all pregnancies (spontaneous miscarriage, elective termination, ectopic pregnancy, normal birth or congenital abnormality) should be followed up and documented even if the subject was discontinued from the study.

If any pregnancy occurs <<in the course of the study>>, then the Investigator or other site personnel informs the appropriate AstraZeneca representatives within 1 day i.e., immediately but **no later than 24 hours** of when he or she becomes aware of it.

The Investigator will ensure that all relevant information is provided to AstraZeneca Patient Safety within 1 or 5 calendar days for SAEs (see Section 0) and within 30 days for all other pregnancies.

The same timelines apply when outcome information is available.

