### **6.8. Management of IP related toxicities**

Study drug will be discontinued. Appropriate supportive treatment should be initiated as dictated by the patient's clinical status.

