#### A Guide to Interpreting the Causality Question

When making an assessment of causality consider the following factors when deciding if there is a ‘reasonable possibility’ that an AE may have been caused by the drug.

- Time Course. Exposure to suspect drug. Has the subject actually received the suspect drug? Did the AE occur in a reasonable temporal relationship to the administration of the suspect drug?
- Consistency with known drug profile. Was the AE consistent with the previous knowledge of the suspect drug (pharmacology and toxicology) or drugs of the same pharmacological class? Or could the AE be anticipated from its pharmacological properties?
- De-challenge experience. Did the AE resolve or improve on stopping or reducing the dose of the suspect drug?
- No alternative cause. The AE cannot be reasonably explained by another aetiology such as the underlying disease, other drugs, other host or environmental factors.
- Re-challenge experience. Did the AE reoccur if the suspected drug was reintroduced after having been stopped? Sponsor would not normally recommend or support a re-challenge.
- Laboratory tests. A specific laboratory investigation (if performed) has confirmed the relationship.

In difficult cases, other factors could be considered such as:

- Is this a recognized feature of overdose of the drug?
- Is there a known mechanism?

Causality of ‘related’ is made if following a review of the relevant data, there is evidence for a ‘reasonable possibility’ of a causal relationship for the individual case. The expression ‘reasonable possibility’ of a causal relationship is meant to convey, in general, that there are facts (evidence) or arguments to suggest a causal relationship.

The causality assessment is performed based on the available data including enough information to make an informed judgment. With limited or insufficient information in the case, it is likely that the event(s) will be assessed as ‘not related’.

Causal relationship in cases where the disease under study has deteriorated due to lack of effect should be classified as no reasonable possibility.

Clinical Study Protocol Appendix E  
Drug Substance Dapagliflozin  
Study Code ESR 17-13124  
Version 8.0  
Date 12JUL2022

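### Section 3.9.1 permits restart of study drug after any resolved, possibly drug-related adverse event, with no exception for ketoacidosis or hypersensitivity, both of which bar a patient at entry

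*Combined protocol and SAP*

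**What the plan says.** The restart rule is in protocol section 3.9.1: "If an adverse event possibly related to the study drug is resolved, subjects will be allowed to re-start the study medication". It makes no distinction by type, severity or seriousness of event and asks for no record of the decision. The same section tells the investigator to take "all possible measures for the safety of the subject".

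Section 3.2 lists among the exclusions "Hypersensitivity to dapagliflozin or any excipients" (criterion 6) and "Recent episode of DKA, frequent episodes of DKA" (criterion 18).

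Other sections that bear on stopping or restarting:

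- Section 3.9 allows discontinuation for adverse events but names none that requires it.
- Section 6.8, on toxicities related to the investigational product, says "Study drug will be discontinued" and does not mention restart.
- Section 3.11 lets the sponsor stop the study for findings that "meet individual stopping criteria or are otherwise considered significant". No such individual criteria are listed in the protocol.
- Section 6.7.1 has the only stop tied to a named event: "Should a pregnancy still occur, the investigational product should be discontinued immediately".
- Appendix A, in its guide to judging causality, remarks: "Sponsor would not normally recommend or support a re-challenge".

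**The concern.** Exclusions 6 and 18 record the protocol's own judgment that these two histories make it unsafe to start dapagliflozin. The restart sentence does not carry that judgment forward. A subject who develops DKA or a hypersensitivity reaction on study, and whose event is judged possibly drug-related and then resolves, falls within the permission as written. The reason for caution is stronger for this subject than for a new one, because the event arose during study treatment and was linked to it.

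The stake is the safety of the individual subject. Either event could be serious on re-exposure.

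**Working it through.** No figure in the plan can be reproduced here, so the main check is to set the texts side by side.

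| Question | Section | What it settles |
|---|---|---|
| May drug be restarted after a possibly related event? | 3.9.1 | Yes, once resolved; no exception |
| May a new subject with drug hypersensitivity start? | 3.2, criterion 6 | No |
| May a new subject with recent or frequent DKA start? | 3.2, criterion 18 | No |
| Must drug be stopped for a product-related toxicity? | 6.8 | Yes; silent on restart |
| Which events stop drug by name? | 6.7.1 | Pregnancy only |
| Is re-challenge discouraged? | Appendix A | Yes in general, but as an aid to judging causality and not as a dosing rule |

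**Does the comparison with entry hold for DKA?** Criterion 18 covers recent or frequent episodes, not any lifetime episode. An on-study episode that has just resolved is recent, so the comparison holds.

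**Do 6.8 and Appendix A close the gap?** Section 6.8 can be read with 3.9.1 as stop first, then restart on resolution, so it sets no bar. The Appendix A remark points the other way from 3.9.1 but does not override it.

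**How often might this arise?** Inputs: n = 30 dapagliflozin subjects (section 8.2) and an assumed probability p that a subject has DKA or a hypersensitivity reaction during treatment. The documents give no rate, so p is an assumption: 0.5%, with a range of 0.1% to 2%.

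- Expected events = 30 × p: 30 × 0.001 = 0.03; 30 × 0.005 = 0.15; 30 × 0.02 = 0.60.
- Chance of at least one = 1 − (1 − p)^30: 1 − 0.999^30 = 0.030; 1 − 0.995^30 = 0.140; 1 − 0.98^30 = 0.455 (0.4545, so 45% to the nearest percent).

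This is the chance of an event. For the restart rule to be faced, the event must also be judged possibly related, must resolve, and must leave a subject able to resume. The 3% to 45% is therefore an upper bound for that arm.

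**What would a bar on restart cost the analysis?** Under 3.10 a permanent stop withdraws the subject from further visits, and 8.3.1 requires both the baseline and the 1-year MRI. Each extra stop before the 1-year MRI thus removes 1/30 = 3.3% of an arm from the primary set. Because the study is blinded, the bar applies to both arms. In the dapagliflozin arm the extra stops are at most 0.03 to 0.60 in expectation. If the placebo arm had the same event rate (a further assumption), the total over 60 subjects would be at most 60 × p = 0.06 to 1.2.

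**The case against.** The case on the other side has real substance.

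- **The sentence is permissive.** It obliges nobody to restart, and 3.9.1 itself puts subject safety first. With 6.8 and Appendix A, the natural default after a serious drug-related event is to stop. This stands: a careful investigator would probably refuse. A reader might infer that the protocol directs re-exposure after DKA; it does not.
- **Section 3.4 extends to receiving medication.** It says that subjects who fail eligibility must neither be enrolled nor be given study drug, without exception. However, its heading and content concern subjects enrolled or randomized in error, and Table 1 appears to place the eligibility check at the first visits only. It may support a refusal but does not clearly govern a restart.
- **Oversight exists.** The Independent Safety Monitor, who is to have endocrinology training, gives a second review of causality (6.3.4), reviews quarterly data and is available for advice between visits (9.2). Serious events go to the funder within 24 hours (6.3.8). None of these steps is required before a restart.
- **The decision need not be blinded.** A reader might infer that restart would be decided without knowledge of assignment. Section 3.7 permits code-breaking in a medical emergency when management requires it, and DKA or anaphylaxis could qualify. Sections 3.7 and 6.5 also provide for unblinding certain serious events that require expedited reporting. These routes may inform the decision but do not bar a restart.
- **Few subjects may benefit.** Version 8.0 is dated July 2022, and section 9.3 gives a planned study period ending March 2021. This stands as a limit on the benefit.

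What remains is that safeguards may prevent an unsafe restart, but no rule does.

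**Conclusion.** The point holds as a gap in a stated rule. Section 3.9.1 permits restart after any resolved, possibly related event, while 3.2 treats two such events as reasons not to start the drug, and nothing in the protocol requires a restart to be refused after either.

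The size is small in frequency. On an assumed event rate of 0.1% to 2%, the chance of at least one such event among 30 dapagliflozin subjects is 3% to 45% (14% at 0.5%), an upper bound on the rule being faced in that arm. The rate has no source in the documents, so the case rests on the seriousness of the events and on the protocol's own entry criteria.

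A reader might go further and infer that the efficacy comparison is compromised, or that subjects were in fact re-exposed. The documents support neither inference: they report no events and do not say whether anyone was still on drug at Version 8.0. Pregnancy is not part of the gap, because 6.7.1 already deals with it. This is a cheap improvement.

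**What to change.** In 3.9.1, replace the restart sentence with:

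> *Study medication will not be re-started after diabetic ketoacidosis or after a hypersensitivity reaction that the Investigator judges possibly related to study medication and clinically significant (e.g. angioedema, anaphylaxis, generalised urticaria). After any other possibly related adverse event that has resolved, it may be re-started if the Investigator documents the decision and its reason.*

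The threshold on hypersensitivity keeps a trivial rash from forcing a withdrawal. For DKA the bar is permanent after one episode, which is somewhat stricter than the entry criterion; that is a deliberate choice. Cross-refer to the new text from 6.8, so that discontinuation and restart agree, and from 3.11, so that the individual criteria it mentions have a place to point to. Section 6.7.1 needs no change.

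The cost is a text amendment with IRB review and no new visits, tests or staff. The downside is the rare extra permanent stop in either arm described above. The change benefits only subjects still on drug or enrolled later under the continuation that 8.2 allows.

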### **3.10 Criteria for withdrawal**

If investigational product is stopped permanently, the subject will be withdrawn from further study procedures/visits (except follow up of adverse events).

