### **Statistical methods**

We will assess changes in myocardial strain and ECV, and T2 relaxation time and their variabilities, any signal on treatment effect with dapagliflozin over at least 1 year using an initial sample size of 60 subjects (n=30 in dapagliflozin group and n=30 in placebo group). Assuming a positive treatment effect on ECV with dapagliflozin at 1 year, a planned “interim” analysis will be performed by an independent group, then, lead to an adaption for a sample size reestimation using variability data generated in this initial group. The investigator(s) will be blinded to subject’s treatment status in this process. We will assess the value and feasibility of continuation of the study subject enrollment to reach a sample size suggested by the “interim” analysis and will allowed to include the initial 60 subjects if a larger sample size is needed. On the other hand, if the “interim” analysis indicates no signal of treatment effect on myocardial strain measurement and ECV with dapagliflozin, further study will not be justified.

Given the exploratory nature of the study, we will analyse the data based on if the treatment is truly received, not be limited to intention to treat comparing dapagliflozin with placebo. Furthermore, we will perform the primary analysis based on proportion of time therapy received as needed.

	PAGE
TABLE OF CONTENTS	
TITLE PAGE .....	1
VERSION HISTORY .....	2
PROTOCOL SYNOPSIS.....	3
TABLE OF CONTENTS.....	5
1. INTRODUCTION .....	12
1.1 Background and rationale for conducting this study .....	12
1.2 Rationale for study design, doses and control groups.....	15
1.3 Benefit/risk and ethical assessment.....	16
1.4 Study Design.....	16
2. STUDY OBJECTIVES.....	17
2.1 Primary objective .....	17
2.2 Secondary objectives .....	17
2.3 Exploratory objectives .....	17
3. SUBJECT SELECTION, ENROLMENT, RANDOMISATION, RESTRICTIONS, DISCONTINUATION AND WITHDRAWAL.....	17
3.1 Inclusion criteria .....	18
3.2 Exclusion criteria .....	18
3.3 Subject enrolment and randomization .....	19
3.4 Procedures for handling incorrectly enrolled or randomized subjects.....	19
3.5 Methods for assigning treatment groups.....	19
3.6 Methods for ensuring blinding.....	19
3.7 Methods for unblinding.....	20
3.8 Restrictions .....	20
3.9 Discontinuation of investigational product.....	20
3.9.1 Procedures for discontinuation of a subject from investigational product .....	20
3.10 Criteria for withdrawal.....	20

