### **3.10.2 Withdrawal of the informed consent**

Patients are free to withdraw from the study at any time (investigational product and assessments), without prejudice to further treatment.

A patient who withdraws consent will always be asked about the reason(s) and the presence of any adverse events (AE). The Investigator will follow up AEs outside of the clinical study. All unused study drug will be returned.

If a subject withdraws from participation in the study, then his/her enrolment/randomisation code cannot be reused. Withdrawn subjects will not be replaced.

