#### **4.2 Treatment period**

All eligible subjects will be randomized at 1:1 to Dapagliflozin 10mg or matching placebo orally once daily at baseline visit. We anticipate <10% of drop out from study enrollment to randomization. The treatment duration is at least 1 year. All study participants will be followed by telephone at 2 weeks and clinically every 3 months, a total of 4 follow-up visits. We will also perform a telephone visit at 2-4 weeks post the study completion to collect information on AE or SAE.

Following Randomization, Physician Randomization Letter will be sent to the subjects' physician(s) describing the study design, subject's participation, medication limitations and contact information for the study PI for any questions.

In the case of abnormal test results, we will contact healthcare providers by phone as soon as the results are available to inform them of the abnormal test results.

Additional glucose management, as needed, using any non-SGLT2 inhibitors or GLP-1 receptor agonists, will be allowed during the study.

In the event of a Public Health Emergency, such as COVID-19 Pandemic, MR service or Clinical space disruptions will be unavoidable. In this case, subjects will be invited to extend study treatment phase until a time that MR service or Clinical space disruptions have ended. This will allow study endpoint measures to coincide with the end of treatment. If treatment phase is extended, subjects will continue on randomized therapy with the same quarterly schedule described in Table 1 with procedures modelled on "3-Month follow-up" and "6-Month follow-up".

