## **8.2. Sample size estimate**

Although a sample size calculation is not possible due lack of available data of changes in myocardial strain, ECV and T2 relaxation time and their variabilities in diabetic patients, we will start a group of 60 qualified subjects for a randomization to dapagliflozin 10 mg (n=30) or matching placebo (n=30) for 1 year. All subjects will undergo cardiac MRI scan at baseline and 1 year. We will assess changes in myocardial strain, ECV and T2 relaxation time and their variabilities, any signal on treatment effect with dapagliflozin. This planned “interim” analysis will be performed by an independent group, then, lead to an adaption for a sample size reestimation using variability data generated in this initial study. The investigator(s) will be blinded to subject’s treatment status in this process. We will assess the value and feasibility of continuation of the study subject enrollment to reach a sample size suggested by the “interim” analysis and will allowed to include the initial 60 subjects if a larger sample size is needed. On the other hand, if the “interim” analysis indicates no signal of treatment effect on ECV with dapagliflozin, further study will not be justified.

The tested hypothesis is that SGLT-2 inhibition with dapagliflozin, in comparison to placebo, will improve myocardial strain, reduce progression of myocardial fibrosis and inflammation in patients with type-2 diabetes.

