## **8.3. Definitions of analysis sets**

### **8.3.1. Efficacy analysis set**

This is primary analysis set for the proposed study and will include any subjects who have both baseline and 1-year follow-up cardiac MRI scans and actually take study medication or placebo.

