### **8.5.5. Sensitivity analysis (if applicable)**

NA.

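### Subjects who permanently stop study drug are withdrawn before their final MRI, so they have no GLS or ECV endpoint for any analysis

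*Combined protocol and SAP*

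**What the plan says.** - **Withdrawal rule (3.10).** "If investigational product is stopped permanently, the subject will be withdrawn from further study procedures/visits (except follow up of adverse events". Restart is allowed once a possibly drug-related adverse event has resolved (3.9.1), so only permanent stops trigger this rule.
- **Scan schedule (8.2, 4.2).** "All subjects will undergo cardiac MRI scan at baseline and 1 year". If a public health emergency extends treatment, the final scan moves with it: "This will allow study endpoint measures to coincide with the end of treatment". No early-termination scan is described.
- **Primary analysis set (8.3.1).** It "will include any subjects who have both baseline and 1-year follow-up cardiac MRI scans and actually take study medication or placebo".
- **Analysis principle (synopsis, Statistical methods).** Citing the exploratory nature of the study, the synopsis says "we will analyse the data based on if the treatment is truly received, not be limited to intention to treat comparing dapagliflozin with placebo". It adds that "we will perform the primary analysis based on proportion of time therapy received as needed".
- **What follows a withdrawal.** "Withdrawn subjects will not be replaced" (3.10.2). Section 8.5.1 plans ANCOVA on 12-month change adjusted for baseline and names no missing-data method. Section 8.5.5 marks sensitivity analysis as not applicable.

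**The concern.** Taken together, these rules define the analysed population by an event that happens after randomisation and may depend on treatment. The protocol names adverse events as a reason to stop drug (3.9), requires a stop for drug-related toxicity (6.8) and counsels every patient about urinary and genital infection (6.3.8). Unequal stopping between arms is therefore plausible, although no rate is given.

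The records would show who stopped and why: reasons for discontinuation (3.9.1), adverse-event withdrawals (6.3.3) and percent missing (8.5). They would not show how stoppers' ECV or GLS changed, so bias from selective or unequal stopping could not be assessed, and it could run for or against the drug. The decision in 8.2 on whether to continue rests on this comparison, and the first 60 subjects may be carried into an enlarged study.

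**Working it through.** **Text check**

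1. GLS and ECV are the primary outcomes, and both are MRI measures (8.4).
2. The only post-baseline MRI is at 1 year or at the end of extended treatment (8.2, 4.2).
3. A permanent stop ends all procedures except adverse-event follow-up (3.10), so the final MRI is not done.
4. The primary set needs both scans (8.3.1), so the subject leaves both primary comparisons.
5. The tests mentioned in 3.9.1 for a subject who discontinues are there for safety, and no MRI is named.
6. The proportion-of-time analysis needs a final scan too. It keeps subjects who interrupt and restart but loses those who stop for good.

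**Illustrative size**

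From the documents: 30 per arm. Assumed: two-sided alpha 0.05, within-group SD 1, active-arm stops pA = 10% or 20% (3 or 6 of 30), and stoppers' mean change differing from completers' by δ = 0.5 or 1.0 SD, equally in both arms. Placebo stops pP are zero, half of pA, or equal to pA. The plan gives no power calculation to reproduce.

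Bias of the completers' difference against all randomised = (pA − pP) × δ. It favours the drug if stoppers do worse and disfavours it if they do better.

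Rejection comes from the noncentral t with noncentrality bias / √(1/n₁ + 1/n₂), where n₁ = 30(1 − pA) and n₂ = 30(1 − pP). Example, 20% vs 0% and δ = 1.0: bias = 0.20; √(1/24 + 1/30) = 0.274; noncentrality = 0.730; rejection = 11.1%.

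For power, take a true all-randomised difference of 0.736 SD, which gives 80% at 30 vs 30. *Lost subjects only* uses the reduced numbers with no bias. *Bias against drug* uses 0.736 minus the bias.

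| pA | pP | δ | Bias (SD) | Rejection, equal groups | Power, lost subjects only | Power, bias against drug |
|---|---|---|---|---|---|---|
| 10% | 0 | 0.5 | 0.05 | 5.4% | 77.8% | 71.9% |
| 10% | 0 | 1.0 | 0.10 | 6.6% | 77.8% | 65.4% |
| 20% | 0 | 0.5 | 0.10 | 6.5% | 75.1% | 62.5% |
| 20% | 0 | 1.0 | 0.20 | 11.1% | 75.1% | 48.5% |
| 10% | 5% | 0.5 | 0.025 | 5.1% | 76.8% | 73.9% |
| 10% | 5% | 1.0 | 0.05 | 5.4% | 76.8% | 70.8% |
| 20% | 10% | 0.5 | 0.05 | 5.4% | 73.0% | 66.9% |
| 20% | 10% | 1.0 | 0.10 | 6.4% | 73.0% | 60.4% |

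With pP = pA the bias is zero and rejection is 5.0%; only precision is lost. If the bias favours the drug with no placebo stops, the chance of a significant result at 0.736 SD is 83% to 92% rather than 80%.

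**The case against.** The strongest reply is that this is a deliberate choice. The synopsis says why the analysis follows treatment received, 8.3.1 and 8.5 match it, and 4.2 extends treatment so that the endpoint is measured on drug. Off-drug scans answer a different question, and the synopsis wording on intention to treat does not commit to a comparison by randomised arm. This is fair as far as it goes. The wording does not exclude that comparison either, and the withdrawal rule also removes permanent stoppers from the proportion-of-time analysis, which the synopsis does plan.

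Several criticisms of the illustration stand:

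- The fall to 48.5% power combines lost subjects with bias. Lost subjects alone account for 80% to 75.1%.
- That fall also needs stoppers to do better than subjects who stay on an effective drug, which is an unlikely pairing.
- The test at 5% is not the decision rule in 8.2, which speaks of a signal and gives no threshold.
- The calculation is unadjusted. The planned ANCOVA would remove any selection explained by baseline values.
- Frequent one-sided stopping is not supported by any figure. The protocol describes an established safety profile and allows restart.

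Section 8.1 also promises a fuller SAP, which could add reporting or sensitivity analyses. It could not create scans that were never taken. A scan at the time of stopping would suit an on-treatment question, but at unequal follow-up times.

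**Conclusion.** The concern holds. From the text alone, every subject who permanently stops before the final MRI is lost to both primary endpoints, and no later analysis can include them. Subjects who interrupt and restart, or who stop after the final scan, are not affected.

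The consequence is uncertain and probably modest. In seven of the eight unequal-stopping cells the rejection rate is 6.6% or less. It reaches 11.1% only with 20% of the active arm stopping, no placebo stops and a full 1 SD difference. All stop rates, differences and effect sizes are assumptions, and the direction of bias is unknown. This is a change the sponsor should make, with medium confidence: the gap in the text is certain and its size is not.

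**What to change.** Amend 3.10 so that a subject who permanently stops drug, has not withdrawn consent and has no medical contraindication to contrast MRI is still invited to the 12-month (or extended end-of-treatment) visit and scan. Report a comparison by randomised arm of all subjects with both scans, whatever their exposure, beside the planned analyses. Report permanent stops, their reasons and missing scans by arm, because some stoppers will not return.

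**Cost.** The change needs an amendment, IRB approval and continued contact with stoppers; the scan is already scheduled for each subject. Off-drug scans dilute the added comparison only. Here 0.736 SD is taken as the on-drug effect, so these powers are not directly comparable with those in the table. If 10% or 20% of the active arm stop and lose the whole effect, it becomes 0.736 × 0.9 = 0.66 SD or 0.736 × 0.8 = 0.59 SD, with power 71% or 61% at 30 vs 30. The on-treatment analyses stay as planned.

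**Partial return still helps.** If half of the active-arm stoppers are scanned and no placebo subject stops, residual bias is (pA − returned/scanned) × δ. In the worst cell this is (0.20 − 3/27) × 1.0 = 0.09 SD instead of 0.20. Across the four cells with no placebo stops it is 0.02 to 0.09 SD, with rejection 5.1% to 6.3%.

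**Limit.** Version 8.0 is dated July 2022, after the study period in 9.3 ended in March 2021, and enrolment status is not given. The number of scans still recoverable is therefore unknown. For any subject whose final visit has passed, only the reporting part applies.
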